1.1 SYNOPSIS

Title: Early N-Acetyl Cysteine treatment for head trauma-induced anosmia

Study Description: This study will compare administration of N-Acetyl Cysteine (NAC) versus

> placebo for the treatment of olfactory loss due to head injury. We hypothesize that treatment with NAC acutely after head injury will result

in improved olfactory function.

Objectives: Primary Objective: To determine if early treatment with NAC after head

injury results in improved olfactory function, compared to placebo.

Endpoints: Primary Endpoint: Olfactory function at 1 and 3 months and post-

enrollment.

Secondary Endpoints: Olfactory-specific quality of life questionnaire. Adult patients of either gender presenting to Ryder trauma center with

Study Population:

mild or moderate blunt head trauma who have abnormal score on

objective olfactory testing.

Phase:

Description of 1.1.1.1.1.1 Ryder Trauma Center at Jackson Memorial Hospital, Miami,

FL. Ryder is a Level 1 trauma center associated with an

academic medical center, the University of Miami.

Description of Study

Sites/Facilities Enrolling

Intervention:

Participants:

[figure not shown]
Subjects will be randomized to receive either NAC or placebo. NAC will be administered orally as a 4 gram loading dose, followed by 2 g PO BID for 4

days, then 1.5 g PO BID for 2 days.

Study Duration: 1.1.1.1.1.2 12 months **Participant Duration:** 1.1.1.1.1.3 3 months

1.2 **SCHEMA**

Prior to Enrollment Total N: Screen potential participants presenting with blunt head trauma, warranting overnight observation, by bedside Smell Identification Test. Subjects with abnormal score will be offered participation in the study and informed consent will be obtained.

1.3 SCHEDULE OF ACTIVITIES (SOA)

Procedur Informed conser		X	Day -2 to 0	Enrollment/Baseline	Day 0	Home treatment	Day 1-6	Study Visit 2	Day 30 +/-7 days	Study Visit 3	Month 4 +/- 3 weeks
Demographics		Х									
Medical history		Χ									
1.3.1.1.1.1	B-IT (Brief olfactio n test)	Х									
1.3.1.1.1.2	SIT (olfactio n test)In person or send by mail.							Х		Х	
1.3.1.1.1.3	QOD (questio nnaire)	Х						Х		Х	
1.3.1.1.1.4	Radiolo gic/Imag ing assessm ent	X									
Randomization		Х									
Physical exam, w	ith nasal	Χ									
endoscopy											
Vital signs		Χ		Χ				Χ		Χ	
1.3.1.1.1.5	Concom itant medicati on review	Х		X				Х		Х	
Pregnancy test		Χ									
1.3.1.1.1.6	Adminis ter study interven tion			Х		Х					
1.3.1.1.1.7	Adverse event review and evaluati on			X				X		Х	

1.4 STUDY RATIONALE

Head trauma is a common cause of permanent olfactory loss. Studies indicate that objective smell loss occurs in 15-35% of traumatic brain injury (TBI) subjects¹. In most cases, olfactory problems do not receive attention until weeks to months following the injury, and the current standard of care is observation, since no specific treatments have been identified². Recently, neuroprotective agents, such as NAC, administered *early* after TBI have gained attention for the potential to promote recovery or prevent long-term neurologic sequelae such as cognitive or vestibular problems³. However, no study has tested whether administration of NAC after TBI can promote recovery of olfactory function. Therefore, we propose to test this simple pharmacologic intervention in TBI patients with objective olfactory loss, identified upon admission to Ryder trauma hospital.

1.5 BACKGROUND

Persistent anosmia (a loss of one's sense of smell) affects an estimated 14 million people in the US⁴. Many persistent acquired forms of anosmia are thought to be due to neurodegenerative processes such as aging (presbyosmia) or damage to the nasal olfactory neuroepithelium (post-viral or post head trauma anosmia)⁵. Of these conditions, patients sustaining head trauma or TBI represent a population of particular interest, since the identification of anosmia in this group may afford us an opportunity to apply an effective intervention in the acute setting. **Currently, we have no treatments for this problem**.

The pathogenesis of head trauma-induced anosmia is incompletely understood. Evidence suggests that blunt trauma causes the brain to move rapidly against the fixed skull base, causing shearing or stretch of the delicate olfactory nerve fibers that project from the nasal cavity through the cribriform plate of the ethmoid bone to connect to the olfactory bulbs of the brain. Furthermore, the trauma can result in bruising or direct injury to the olfactory bulbs, among other intracranial injuries. The end result appears to be a rapid degeneration and death of the primary olfactory receptor neurons, situated in the olfactory epithelium of the nose. Biopsies of human nasal olfactory tissue from such anosmia patients often show neurodegenerative changes, strongly supporting the notion that loss of function is related to damage to the nasal neuroepithelium⁵. Despite an ability of basal cells in the olfactory epithelium to produce new neurons⁶, many TBI patients do not regain olfactory function, suggesting that after injury the axons fail to properly reinnervate the olfactory bulbs. It is believed that intracranial scarring, or reactive gliosis, develops as a response to the degenerative changes and may prevent reinnervation. We hypothesize that an early intervention to prevent degeneration (olfactory neuron apoptosis) and the accompanying glial scarring would help promote olfactory recovery following TBI.

In considering possible therapeutic compounds, NAC is an attractive candidate for several reasons. It is FDA approved for both systemic and topical respiratory administration and has a long track record of safe clinical use. Also, research in other tissue systems has provided strong data supporting its neuroprotective effects⁷. For instance, in animal models of inner ear sensory damage or degeneration,

NAC is effective at promoting recovery of neurons⁸. Finally, a recent human clinical trial tested oral NAC administration for neuroprotective effects following traumatic brain injury and found it to be safe and effective³. In that study, olfaction was not assessed, but other neurologic outcomes such as cognitive and vestibular function were markedly improved. We plan to use the same dosage regimen that was used in that study. Since animal modeling of olfactory injury, such as methimazole or methyl bromide induced lesion or olfactory bulbectomy results in robust regeneration^{9,10}, testing of medications for regenerative efficacy is not feasible. Given the safety and efficacy of NAC therapies in animals and humans in other tissue systems, we propose to undertake a human study testing acute NAC therapy for treatment of TBI-induced anosmia. Identification of an effective therapy for certain forms of anosmia would be a significant advance, as there currently are no treatments available.

1.6 RISK/BENEFIT ASSESSMENT

1.6.1 KNOWN POTENTIAL RISKS

Risks from medication: NAC is FDA approved, with a forty-year safety history. It is widely used for nebulized delivery to the lower airways for its mucolytic effects (Mucomyst). Otolaryngologists have prescribed NAC off-label as a topical nasal medication for years for certain chronic rhinosinusitis patients for it mucolytic effects, with no safety concerns reported. It also has a long history of systemic oral administration safely. It is used at high dose orally in emergency departments for acetaminophen overdose, to prevent hepatotoxicity. Known side effects reported from nebulized pulmonary delivery include some patients reporting a noticeable odor. Other possible side effects might include local irritation; however it has been used widely in the lower airways and via tracheostomy stoma without irritation. There are rare reports of bronchospasm reactions to NAC delivered to the lower airways via nebulizer; these typically respond to bronchodilators (albuterol). Loading doses for FDA-approved oral administration of NAC are about 55 ml of 20% NAC solution (≈10 g), and our study patients will receive a 4 g loading dose, much lower. Importantly, a recent published study using the identical oral NAC regimen proposed here reported no adverse events or treatment side effects³. NAC can cause headache or potentiate effects of nitroglycerine or isosorbide. It may alter levels of homocysteine. It may potentiate the effects of certain immunosuppressants, such as cyclophosphamide or azathioprine. It can cause GI upset.

Other risks: There is no economic risk, as we will supply the study medication. The pre-study work up and care is the trauma standard-of-care, unchanged, and is no different for patients choosing or not choosing to participate in this study. Psychologically, there is the risk of disappointment from possible lack of improvement or from treatment with placebo. However, the current standard-of-care is **no treatment**, so we will council patients regarding this.

1.6.2 KNOWN POTENTIAL BENEFITS

The immediate and long-range potential benefit is improvement in olfactory function. As stated, the standard of care for TBI induced anosmia is observation, and many patients do not recover olfaction. Basic cell culture and animal studies with NAC, as well as a recent human trial of NAC following TBI, support the conclusion that NAC can prevent neuronal degeneration or cell death and promote neural recovery or regeneration. Thus, there is potential that olfactory neuron damage following TBI, which leads to anosmia, will improve with NAC treatment in this study. Secondary potential benefits include improvement in other non-olfactory TBI sequelae such as headache, cognitive dysfunction or vestibulopathy, as reported in a recent NAC trial for TBI.

1.6.3 ASSESSMENT OF POTENTIAL RISKS AND BENEFITS

Existing evidence is consistent with a very positive risk to benefit assessment. Prior clinical trial with the exact NAC regimen in TBI patients reported no adverse effects. The treatment involves only a 1 week course of therapy. There are no existing alternatives. Basic science studies provide a wealth of evidence for promoting neuronal recovery using this drug.

OBJECTIVES AND ENDPOINTS

OBJECTIVES		ENDPOINTS		JUSTIFICATION FOR ENDPOINTS		
Primary						
To determine if early treatment with NAC after head injury results in improved olfactory function, compared to placebo.		1.6.3.1.1.1.1	Olfactory function at 1 and 3 months post- enrollment, as measured by Smell Identification Test (SIT).	1.6.3.1.1.1.2	sIT is a validated test for olfaction. Time points of 1 and 3 months were chosen to test for early recovery of olfactory neurons versus evidence for successful regeneration, respectively.	
Secondary						
1.6.3.1.1.1.3	To assess olfactory- specific quality of life measure in treated versus placebo groups.	1.6.3.1.1.1.4	Questionnaire on olfactory dysfunction (QOD) scores at 1 and 3 months.	1.6.3.1.1.1.5	QOD is a validated tool for measuring quality of life related to olfactory loss.	

OBJECTIVES	ENDPOINTS	JUSTIFICATION FOR ENDPOINTS
Tertiary/Exploratory		
N/A		

STUDY DESIGN

1.7 OVERALL DESIGN

- **Hypothesis**: Early treatment with NAC after head injury will result in improved olfactory function, compared to placebo.
- Phase 2 trial.
- **Design:** Randomized, placebo-controlled, double-blind study.
- Study groups: Treatment versus Placebo.
- Number of Sites: Single site.
- Study Intervention: N-Acetyl-Cysteine (NAC)

1.8 SCIENTIFIC RATIONALE FOR STUDY DESIGN

We seek to determine if early treatment with NAC will improve olfaction in TBI patients with olfactory loss. To obtain high quality evidence, we chose a prospective randomized placebo control double blind approach. There is no standard of care treatment or drug that can be used for comparison; the current standard of care is observation. To avoid bias, a double blind approach will be used. Based on the best knowledge for mechanism of olfactory loss in TBI patients, we believe that the best chance for efficacy is to identify and treat patients as soon as possible following injury. Therefore, the protocol is designed to test olfaction in an acute trauma setting and test intervention acutely.

1.9 JUSTIFICATION FOR DOSE

Dose regimen is based on a prior clinical study of acute TBI patients³. In that study, no adverse effects were identified. Although olfaction was not assessed, the dose was found to be efficacious for their specific measures, including common TBI sequelae such as dizziness, headache, or memory problems.

1.10 END OF STUDY DEFINITION

The end of the study is defined as completion of the last visit shown in the SoA.

STUDY POPULATION

1.11 INCLUSION CRITERIA

In order to be eligible to participate in this study, an individual must meet all of the following criteria:

- Admitted to Ryder Trauma Center for observation acutely following head injury (i.e. concussion), with documented hyposmia or anosmia by University of Pennsylvania Brief Smell Identification Test (SIT). (The Brief smell identification test B-SIT is a rapid and effective 5 minute screening test. This 12 item version of the Smell Identification Test is useful for detecting smell loss in situations where less than five minutes of time are available)
- 2. Male or female, aged 18 years or older
- 3. Provision of signed and dated informed consent form
- 4. Stated willingness to comply with all study procedures and availability for the duration of the study
- 5. Ability to take oral medication and be willing to adhere to the NAC regimen
- 6. For females of reproductive potential: use of highly effective contraception for at least 1 month prior to screening and agreement to use such a method during study participation and for an additional 4 weeks after the end of NAC administration

1.12 EXCLUSION CRITERIA

An individual who meets any of the following criteria will be excluded from participation in this study:

- 1. Severe trauma requiring ongoing inpatient treatment beyond 48 hours
- 2. Pregnancy (based on urine screening) or lactation
- 3. Known allergic reactions to components of NAC, such as Mucomyst
- 4. Currently taking nitrates such as nitroglycerine and/or isosorbide regularly
- 5. Currently taking azathioprine (Imuran) or cyclophosphamide (Cytoxan)
- 6. Known diagnosis of cystinuria (renal condition in which cysteine supplement should be avoided)
- 7. Febrile illness within 1 week
- 8. Treatment with another investigational drug or other intervention within 3 months
- 9. Active sinonasal disease by imaging and/or nasal exam, i.e. rhinosinusitis, nasal polyps
- 10. Adults unable to consent
- 11. Prisoners, employees or subordinates
- 12. Individuals who are not yet adults (infants, children, teenagers). This population is excluded because efficacy has not yet been established in adults.

1.13 LIFESTYLE CONSIDERATIONS

N/A

1.14 SCREEN FAILURES

Screen failures are defined as participants who consent to participate in the clinical trial but are not subsequently randomly assigned to the study intervention or entered in the study. A minimal set of screen failure information is required to ensure transparent reporting of screen failure participants, to meet the Consolidated Standards of Reporting Trials (CONSORT) publishing requirements and to respond to queries from regulatory authorities. Minimal information includes demography, screen failure details, eligibility criteria, and any serious adverse event (SAE). Re-screening will not be performed.

1.15 STRATEGIES FOR RECRUITMENT AND RETENTION

- Target study sample size: 30 subjects in each arm, 60 subjects total. No exclusions by gender, race and ethnicity. Anticipated number to be screened in order to reach the target enrollment: 300 subjects (approximately 33% of trauma subjects may have abnormal SIT scores; of these, approximately 40% may have other exclusions or decline).
- Anticipated accrual rate: 60 subjects
- Anticipated number of sites: 1
- Source of participants: inpatient hospital setting, Ryder Trauma unit. The potential study subjects will be identified from patients under the care of the Investigators' team at Ryder Trauma. Potential participants will be selected by identifying subjects admitted for observation at Ryder Trauma Center following blunt head trauma.
- Types of recruitment strategies planned: N/A, subjects will be identified from inpatient population as described, and approached regarding possible participation prior to discharge.
- Incentives for visit attendance: patients will need to follow up in Otolaryngology clinic at approximately 1 and 3 months. To improve retention, they will be offered a payment incentive of \$50 for attending these visits; paid upon completion of the visit, prorated if not complete.
- Specific strategies that will be used to recruit and retain historically under-represented populations in order to meet target sample size and conform with the NIH Policy on Inclusion of Women and Minorities as Participants In Research Involving Human Subjects: We will not exclude any demographic (other than children, as stated); our population in Dade County is quite diverse; the study population is anticipated to reflect this diversity, including a majority of Hispanic subjects.

STUDY INTERVENTION

1.16 STUDY INTERVENTION(S) ADMINISTRATION

1.16.1 STUDY INTERVENTION DESCRIPTION

Subjects will be randomized to receive either N-Acetyl-Cysteine (NAC) or placebo, to be prepared and packaged by our research pharmacy. NAC will be administered orally as a 4 gram loading dose, followed by 2 g PO BID for 4 days, then 1.5 g PO BID for 2 days.

NAC is available as a generic over-the-counter oral supplement. It is not FDA regulated. Since there is **not** an FDA-approved labeling for over-the-counter oral NAC use, our trial does not change any existing label. NAC is also the active ingredient in the drug Mucomyst. Mucomyst is used as a pulmonary inhaled nebulized drug for its mucolytic properties to help treat chronic bronchitis. NAC is also administered orally or by nasogastric tube in Emergency Departments for the treatment of acetaminophin (Tylenol) overdose.

1.16.2 DOSING AND ADMINISTRATION

NAC or placebo will be administered orally as a 4 gram loading dose, followed by 2 g PO BID for 4 days, then 1.5 g PO BID for 2 days. The loading dose will be given prior to discharge from Ryder Trauma center. Remaining doses will begin on the following morning as an outpatient to complete the 1 week treatment course. Delayed doses may be taken late if noted before the next dose, and otherwise will be skipped. The doses may be taken with or without meals.

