1.22 PARTICIPANT DISCONTINUATION/WITHDRAWAL FROM THE STUDY

Participants are free to withdraw from participation in the study at any time upon request.

An investigator may discontinue or withdraw a participant from the study for the following reasons:

- Pregnancy
- Significant study intervention non-compliance
- If any clinical adverse event (AE), laboratory abnormality, or other medical condition or situation occurs such that continued participation in the study would not be in the best interest of the participant
- If the participant meets an exclusion criterion (either newly developed or not previously recognized) that precludes further study participation

The reason for participant discontinuation or withdrawal from the study will be recorded on the NAC Case Report Form (CRF). Subjects who sign the informed consent form and are randomized but do not receive the study intervention may be replaced. Subjects who sign the informed consent form, and are randomized and receive the study intervention, and subsequently withdraw, or are withdrawn or discontinued from the study, will be replaced. Patients who do not complete the full course of study drug/placebo will be noted in the results tables, and they will not be included in the statistical analysis of outcome measures, since this is a simple comparison of SIT score between patients receiving a 1 week course of NAC versus placebo.

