1.29 SAMPLE SIZE DETERMINATION

Number of participants to enroll to have adequate power to test the key hypotheses for the study:

Placebo group: 30 Treatment group: 30

- Target study sample size: 30 subjects in each arm, 60 subjects total. Anticipated number to be screened in order to reach the target enrollment: 300 subjects (approximately 33% of trauma subjects may have abnormal SIT scores; of these, approximately 40% may have other exclusions or decline).
- Outcome measure used for calculations: SIT score
- Test statistic: t-test
- Null and alternative hypotheses:

Null hypothesis: There is no difference in SIT score with NAC treatment or placebo.

Alternative hypothesis: NAC treatment results in improved SIT score.

• Type I error rate (alpha): 0.05

Power level: 0.8

• Assumed mean and variance: Placebo group, mu1: SIT=17 ± 10

Treatment group, mu2: SIT=25 ± 10

Reference: "Hypothesis Testing: Two-Sample Inference - Estimation of Sample Size and Power for Comparing Two Means" in Rosner, Bernard Fundamentals of Biostatistics, Belmont, Calif.: Duxbury Press, [1995].

SIT score of 17 is used for the placebo group because this is at the upper range of a score categorized as anosmia (total loss of olfaction). In a recent large review and meta-analysis of TBI-induced olfactory loss¹ a range of SIT scores are reported in the 7-27 score range, for mild-moderate TBI. Based on these data, we anticipate identifying and enrolling patients with a mean score of approximately 17 and a variance of approximately 10.

In terms of estimated possible improvement in SIT score with NAC treatment, we have chosen an increase of 8 ± 10 points, because a jump of more than a few points on a repeat SIT test after one

month is considered to be greater than just random chance¹¹; (and [name], *personal communication*). There are no published data available for specifically measuring olfactory change following treatment with NAC for head trauma. In a pilot study testing topical intranasal NAC for different forms of anosmia (Clinicaltrials.gov), no published results are available. However, in a study using the same dosage regimen of oral NAC following blast TBI and assessing non-olfactory outcome measures, quantifiable neuropsychiatric measures did show a roughly 25-33% improvement versus placebo, providing an additional indirect basis for expecting a similar magnitude effect on our measures³.

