1.31.2 ANALYSIS OF THE PRIMARY EFFICACY ENDPOINT(S)

Primary endpoint is SIT score at 1 month and 3 months.

Placebo and NAC-treated groups will be compared. SIT (mean ± sd) will be compared via two-tailed t-test.

SIT scores may range from 0-40, and normal scores are well-established. An assignment of normosmia, mild hyposmia, moderate hyposmia, severe hyposmia, anosmia, or probable malingering can be made based on SIT score.

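### Section 1.16.2 allows doses to be skipped, yet 1.22 drops anyone short of an undefined full course; read literally, patients who followed instructions leave the outcome analysis

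*Combined protocol and SAP*

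**What the plan says.** Four places in the combined protocol and SAP bear on how much study drug a patient must take to count in the analysis.

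- **1.16.2 (dosing and administration):** after the loading dose, patients take study drug twice daily for 4 days and then twice daily at a lower dose for 2 days. On missed doses: "Delayed doses may be taken late if noted before the next dose, and otherwise will be skipped". A skipped dose therefore conforms to the protocol.
- **1.22 (withdrawal), list of grounds:** an investigator may withdraw a participant for "Significant study intervention non-compliance". The qualifier implies that minor non-compliance is tolerated.
- **1.22, closing sentence:** "Patients who do not complete the full course of study drug/placebo will be noted in the results tables, and they will not be included in". What they are left out of is the outcome analysis. No number or percentage of doses is attached to the full course.
- **1.30 (populations):** the only named set is intention-to-treat, meaning all randomized participants, 30 per arm.

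Three other provisions matter. Section 1.22 says that treated participants who later withdraw or are withdrawn will be replaced. Dose-taking is recorded in a self-kept log without assay (1.19), and patients who miss doses are to return unused product (1.17.1). The sample size section adds 5 per group for dropout, withdrawal and missing data together (1.29).

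**The concern.** A patient who forgets one home dose, notices too late and skips it has done what 1.16.2 says. That patient is not obviously a case of significant non-compliance, yet on the plain words of 1.22 did not take the full course and leaves the SIT and QOD comparisons. Because the term is undefined, two analysts could build different analysis sets from the same logs.

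Two things are at stake.

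**Selection.** Completion is determined after randomization, so excluding on it gives up the protection that randomization provides. The protocol itself gives reasons why skipping might differ by arm: 1.9 lists memory problems among common sequelae of head injury, the background (1.5) reports better cognitive outcomes with NAC in the earlier trial, and 1.6.1 lists gastrointestinal upset as an NAC effect. These could act in opposite directions, so the sign of any bias cannot be predicted.

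**Numbers.** With 12 doses at risk, a low skip rate per dose can become a sizeable share of patients with at least one skip. Those patients would draw on the same 5 per arm that is meant to cover real dropout and missing outcomes.

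**Working it through.** **Inputs.** From 1.29: "Type I error rate (alpha): 0.05", "Power level: 0.8", "Placebo group, mu1: SIT=17 ± 10" and "Treatment group, mu2: SIT=25 ± 10", so the difference is 8 with SD 10. From 1.31.2, a two-sided test: "SIT (mean ± sd) will be compared via two-tailed t-test". From 1.29 again: 30 per arm, including 5 for losses. Home doses from 1.16.2: 4 × 2 + 2 × 2 = 12. The per-dose skip rate p is not in the documents and is assumed over a range.

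**The plan's own figure.** n per arm = 2 × [10 × (1.960 + 0.842) / 8]² = 24.5, rounded up to 25; 25 + 5 = 30, which matches. The exact t calculation needs 26. Noncentral-t power is 86% with 30 analysed per arm and 79% with 25.

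**Share excluded if any skip counts as non-completion.** With independent skips, P(at least one of 12) = 1 − (1 − p)^12. Power is noncentral-t at the expected number left, with no other losses and no replacement.

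| p per dose | Excluded | Lost per arm | Left per arm | Power |
|---|---|---|---|---|
| 0.5% | 5.8% | 1.8 | 28.2 | 84% |
| 1% | 11.4% | 3.4 | 26.6 | 82% |
| 2% | 21.5% | 6.5 | 23.5 | 77% |
| 3% | 30.6% | 9.2 | 20.8 | 71% |
| 5% | 46.0% | 13.8 | 16.2 | 60% |

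**Break-even.** Losing 5 of 30 requires 1 − (1 − p)^12 = 5/30, so p = 1 − (25/30)^(1/12) = 1.5%. At p = 2%, the chance that a given arm loses more than 5 is P(Binomial(30, 0.215) ≥ 6) = 65%.

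**With loss to follow-up as well.** At an assumed 10% loss and p = 1%, 30 × 0.90 × 0.99^12 = 23.9 per arm remain, with power of 77%.

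**If skips cluster within patients.** Take a beta-binomial model with an assumed within-patient correlation of 0.2, so that a + b = 1/0.2 − 1 = 4 and a = 4p. The chance of no skip is the product over j = 0 to 11 of (b + j)/(4 + j). At p = 2%, 11% are excluded, 26.6 per arm remain and power is 82%. At 3%, 16.5% are excluded, 25.1 remain and power is 79%.

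**If some skips are tolerated.** At p = 5% with independence, P(2 or more of 12) = 11.8% and P(3 or more of 12) = 2.0%. Tolerating one skip would thus exclude about 12% of patients, and tolerating two about 2%.

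**The case against.** The strongest objection is that 1.22 never says a skipped dose makes a patient a non-completer. Section 1.16.2 speaks of completing the one-week course and shortly afterwards allows skips, so a skip may sit inside completion. The sentence in 1.22 comes in a section on withdrawal and can be read as aimed at early stopping. This stands in part: zero tolerance is the literal reading, not an explicit rule. It does not settle the matter, because no section gives the milder reading either.

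A reader might infer that one skip can exhaust the dropout allowance. It cannot: one skip costs one analysable patient, and it takes five such patients in an arm.

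A reader might also infer that the planned power will not be reached. The documents do not support that. The skip rate is unknown, power stays above 80% at 1% per dose under independence, and clustering, which is plausible if forgetfulness differs between patients, roughly halves the exclusions at 2%. If 1.30 governs and every outcome is obtained, nobody is excluded and power is 86%.

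Replacement under 1.22 could restore the numbers. Whether it covers a patient who skips a dose but stays in follow-up is unclear, and replacing patients would not undo selection after randomization.

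The drug log is not the only source for dose counts, since returned product is a second one. However, the log is collected at the first outpatient visit, and the mail option in 1.26.8 covers only the SIT and QOD, so the plan does not say how completion is established for patients followed by mail.

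**Conclusion.** The concern holds as a conflict between sections and an undefined exclusion. Section 1.16.2 treats a skip as conforming, the closing sentence of 1.22 read literally removes the patient from the outcome analysis, and 1.30 keeps every randomized patient. The selection problem follows from the exclusion itself and does not depend on how many patients skip, though its direction and size cannot be determined from the documents.

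The effect on numbers is conditional. It requires that 1.22 overrides 1.30, that any skip counts, and that skippers are not replaced. Under those conditions and independent skips, rates from 1% to 5% per dose exclude 11% to 46% of patients and give power from 82% down to 60%, with the allowance used up at about 1.5%. The rates and the independence are assumptions. A shortfall is possible at modest skip rates but is not shown to be likely.

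**What to change.** Reconcile 1.16.2, 1.22 and 1.30 for the analysis:

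1. State in 1.30 and 1.31 that all randomized patients with outcome data enter the primary SIT and QOD comparisons in their assigned arm, regardless of skipped doses.
2. In 1.22, replace the exclusion of those who do not take the full course with an analysis-only completer definition, fixed before unblinding, that does not count skips permitted by 1.16.2. One form is to class as a non-completer only a patient who stopped study drug for good before the course ended. If a minimum dose count is also wanted for the analysis set, give it as a number; the one-skip and two-skip figures above show what such a choice would exclude.
3. Derive this status from the drug log and returned product, say how both are obtained from patients followed by mail, and use it only for a supportive per-protocol analysis.

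No change is needed to the dosing instruction or to the criteria for withdrawing participants. The cost is a few sentences in 1.22, 1.30 and 1.31, using records already planned apart from the arrangement for mail follow-up. The downside is that the completer set will include some patients with slightly less than full exposure.
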